## List of acronyms

Ab	Antibody
APRI	AST to platelet ration index
ART	Antiretroviral therapy
CHC	Chronic Hepatitis C infection
DAA	Direct-acting antiviral agent
DCV	Daclatasvir
ECHO	Extension for Community Healthcare Outcomes
HCV	Hepatitis C virus
HIV	Human Immunodeficiency Virus
PWID	People Who Inject Drugs
Lab	Laboratory
MOH	Ministry of Health
MSM	Men who have sex with men
OAT	Opioid agonist therapy
PWID	People who inject drugs
PLWH	People living with HIV
PCR	Polymerase chain reaction
RBV	Ribavirin
RNA	Ribonucleic acid
SHIM	simplified HCV care and treatment model
SOC	Standard of care
SOF	Sofosbuvir
SVR12	Sustained viral response at week 12
VEL	Velpatasvir
VL	Viral load
WHO	World health organization

## Summary

About 12,000 patients receive opioid agonist treatment in Ukraine, 83% of them are HCV-infected. Considering the rapidly increasing availability of DAA medications in Ukraine, this group can be efficiently covered with treatment using a simplified integrated HCV care model. The goal of the proposed project is to adapt and evaluate the effectiveness of a simplified HCV care and treatment model (SHIM) integrated into OAT clinics in Ukraine, using hybrid type 2 implementation science approach. SHIM implementation will be strengthened by Project ECHO (Extension for Community Healthcare Outcomes), a collaborative telehealth learning intervention, supporting and empowering clinicians to develop knowledge and self-efficacy about HCV care, which has not traditionally been integral to their scope of practice. As an implementation study, our project will generate much needed process data and clinical evidence for rapid scale-up of integrated HCV treatment in Ukraine and other countries of the region.

The Stage 1 aims are:

- 1) To develop SHIM and demonstrate its feasibility. We will develop the SHIM manual, train clinicians and conduct a pilot test with 20 OAT patients with HCV infection at an OAT clinic.
- 2) Using a multi-level implementation science framework, to examine the client, clinician and organizational factors that contribute to SHIM adoption and clinical outcomes.

If the pilot demonstrates feasibility and continuation is approved, the Stage 2 aim is:

- 3) To evaluate the effectiveness of SHIM in improving the HCV treatment cascade outcomes using a cluster-randomized three-arm trial design in 480 HCV-infected patients at 12 OAT clinics (4 clinics per arm) randomized to standard of care (N=160) versus SHIM with (N=160) or without (N=160) ECHO facilitation.

The primary outcomes of both pilot and main study phases are based on the HCV treatment cascade: (a) Completing the pretreatment evaluation; (b) Initiating and completing the full DAA course; (c) Achieving SVR12. Secondary outcomes will include treatment motivation, adherence, quality of life, treatment satisfaction. Although not sufficiently powered, we will measure re-infection rates among those achieving SVR.

Stage 1 is focused on feasibility and does not include hypothesis testing. In Stage 2 trial, we will test two main hypotheses (1) SHIM clinics will have better adoption and penetration of HCV care elements, that will ultimately result in improved patient-level outcomes like HCV cure compared to standard of care; (2) Compared to No-ECHO, ECHO-facilitated sites will have improved HCV cascade outcomes.

The results of the model evaluation, if proven effective, will allow us to advocate for its scale-up to other non-specialized settings in Ukraine and internationally and contribute to HCV elimination.

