### 3.5.4 Primary Endpoints

Primary outcomes are based on the HCV treatment cascade:

- P1. Completing pretreatment evaluation (completing all clinical and laboratory assessment prescribed by the physician according to the SHIM algorithm);
- P2. Initiating DAA treatment (taking the first dose of DAA medication prescribed by the physician);
- P3. Achieving SVR12 (having an undetectable HCV RNA PCR result at 12 weeks after treatment completion).

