### 3.5.5 Secondary Endpoints

Secondary outcomes will include the interim cascade steps:

- S1a. Testing for HCV RNA;
- S1b. Assessment of fibrosis staging;
- S1c. Completion of DAA treatment (receiving the last prescribed medication supply);
- S1d. Testing for HCV RNA at 12 weeks after treatment completion;

Factors that affect treatment effectiveness:

- S2a. DAA treatment motivation (summary score measured by the investigator-developed questionnaire at baseline);
- S2b. DAA treatment adherence (defined as percentage of doses taken using two measures: visual analog scale administered at treatment completion, and pill counts at each dispensing visit);
- S2c. Treatment satisfaction (measured by investigator-developed questionnaire at treatment completion);

Treatment outcomes:

- S3a. Quality of Life (measured by SF-12 questionnaires at all four interviews);
- S3b. Re-infection (measured at 12 months after treatment completion among those achieving SVR).

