### 3.5.8 Analytic plan

All analyses will be according to the principle of intent-to-treat, i.e., analysis of site and individuals within the site as randomized. The primary individual-level outcomes are achieving three elements of the HCV treatment cascade (diagnosed, treated, achieving SVR). We have powered the study based on a comparison of the proportions among the three groups (see below). The denominator for all cascade indicators is the number of OAT patients who are screened positive for HCV and are enrolled in the study. The numerators, the number who completed the pre-treatment evaluation, started DAA treatment and achieved SVR, will be obtained from the electronic clinical data collection system. Data will be assessed for missingness. A repeated measures likelihood based mixed model with missing at random (MAR) assumptions will be used for the analysis of the primary outcome to compare the three allocations, adjusted for the stratification variables (geographic region) plus age and gender. We will also adjust for covariates that are predictive of missingness to be consistent with the MAR assumption. Sensitivity analyses as described below will be done to assess this assumption, which is a reasonable starting point given missing data is expected to be low. Results will be displayed as point estimates with corresponding 95% confidence limits. The primary (and secondary) outcomes will be tested at the 5% (2-sided) significance level.

Hypotheses

1) OAT facilities implementing the simplified integrated model will have adoption and penetration of HCV care elements, that will ultimately result in improved patient-level outcomes like HCV cure compared to standard of care (SOC);

2) Compared to No ECHO, clinicians at ECHO-facilitated sites will have improved HCV care cascade outcomes.

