Aim 3's analysis will involve three distinct strategies. First, we will examine the time difference in HCV cascade elements (% diagnosed, % treated, % achieving SVR), with sub-analyses for geographic area and OAT dropout +/- ECHO vs SOC setting. To do this, we will use a generalized mixed linear model (with a logit link), where group will vary by either study arm or by geographical area. Our dependent variables will include: 1) a binary indicator for whether an individual patient achieved the desired HCV diagnosis/treatment coverage cut-off (e.g. diagnosis coverage >80%), as previously used to measure comprehensive and holistic integrated primary care for PWID receiving buprenorphine [42]. The same approach will then be used for secondary individual outcomes (treatment motivation and adherence, treatment satisfaction, quality of life), which we have done previously when integrating addiction treatment into specialty services in the US [43] and Ukraine [12]. 2) treating the primary and secondary indicators as a continuous variables. Any changes in national guidelines that might influence HCV treatment availability would not be scored until after at least 1 year after publication in order to allow for uptake changes by clinicians. Our covariates will include time trends, client-level variables including demographic characteristics, fibrosis stage, treatment motivation and adherence, addiction severity and mental health measures, as well as organizational and provider level measures (from Aim 2).

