In addition, we have planned to test for a linear trend among the intervention levels for the proposed outcomes, testing that SHIM+ECHO > SHIM with No ECHO > SOC. We also plan to test the treatment effects using similar methods for OAT dropout strata separately. In addition to direct effects, mediation and moderation regression will be conducted as described by Donaldson. Testing will be conducted at a Bonferroni corrected type I error level of 0.025 to control for multiple testing. Secondary and process outcomes will similarly be tested. These measures and their subscales will be compared as pre/post and over time using one-way ANOVA/Duncan test, with general linear models to identify differences in treatment effect stratified by the geographic region (cluster). Mean scores will be normalized, with comparisons between the three groups, with the referent being SOC. To address multiple testing, we will use the Benjamini-Hochberg method of controlling the false discovery rate. We do not expect missing data to be a concern since most of the data on primary outcomes will be derived from clinical source documentation; for the survey data, we expect that we will collect more than 90% of the data at the 24-week time point. We will, however, explore all patterns of missing data and compare those with and without data to determine whether the data may be MAR or not MAR (i.e. eliminate the missing completely at random assumption). We will conduct sensitivity analyses using an appropriate missing data method, such as multiple imputation.

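### Re-infection (S3b) falls under the blanket testing rules although it is underpowered and restricted to patients with SVR, a group formed after randomisation by a primary endpoint

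*Combined protocol and SAP*

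**What the plan says.** The Summary names some secondary outcomes ("Secondary outcomes will include treatment motivation, adherence, quality of life, treatment satisfaction") and then mentions re-infection separately: "Although not sufficiently powered, we will measure re-infection rates among those achieving SVR". It mentions no test.

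Section 3.5.5 lists re-infection as S3b, under treatment outcomes: "Re-infection (measured at 12 months after treatment completion among those achieving SVR". The group in which it is measured is defined by primary endpoint P3 in section 3.5.4: "Achieving SVR12 (having an undetectable HCV RNA PCR result at 12 weeks after treatment completion".

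Section 3.5.8 has two general testing statements. One stands in the paragraph on the comparison of the three allocations: "The primary (and secondary) outcomes will be tested at the 5% (2-sided) significance level". The other comes after the paragraph on the mixed model: "Secondary and process outcomes will similarly be tested". Neither makes an exception for S3b. The same section sets all enrolled screen-positive patients as the denominator, but only for the cascade indicators.

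No sentence gives a model, a denominator or a test specific to S3b. Section 3.2 says the 12-month re-infection test will be recommended and its cost reimbursed.

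**The concern.** Only a cured patient can be re-infected, so SVR achievers are the natural risk set for a descriptive rate. They are not a valid basis for a randomised comparison when the arm affects who enters the set. Hypothesis 1 is that SHIM ends in more cures than SOC. If it does, the SHIM arms' SVR group contains patients of a kind who would not have been cured under SOC, and the groups may differ in re-infection risk for that reason alone. Adjusting for region, age and gender does not restore the balance.

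An analyst who follows 3.5.8 literally would test S3b by arm. Two misreadings could follow. A non-significant result could be taken as evidence of no difference. A difference in observed rates, in either direction, could be credited to integrated care when it reflects only who was cured. The Summary says the results, if favourable, will be used to argue for scale-up, so either misreading would matter.

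**Working it through.** **Plan's own figure.** There is none for S3b. Section 3.5.9 sizes the trial for the primary comparison of proportions and gives no event rate or power for re-infection. Only the arm size (160 per arm, 4 clinics each) comes from the documents. All SVR and re-infection rates below are assumptions.

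**Step 1: selection with no effect on re-infection.** Let s0 and s1 be the SVR proportions in SOC and SHIM. Assume that everyone cured under SOC would also be cured under SHIM, with 12-month risk a, and that patients cured only under SHIM have risk b. The arm changes nobody's risk. Then

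- SOC observed risk = a
- SHIM observed risk = [s0 × a + (s1 − s0) × b] / s1

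With s0 = 0.30, s1 = 0.70, a = 3% and b = 10%: (0.30 × 3 + 0.40 × 10) / 0.70 = 7.0% against 3.0%, a ratio of 2.33.

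| SVR SOC / SHIM | a = 3%, b = 10% | a = 5%, b = 10% | a = b = 5% | a = 10%, b = 5% |
|---|---|---|---|---|
| 30% / 70% | 2.33 | 1.57 | 1.00 | 0.71 |
| 20% / 80% | 2.75 | 1.75 | 1.00 | 0.63 |
| 50% / 80% | 1.88 | 1.38 | 1.00 | 0.81 |

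A milder contrast gives a smaller distortion: with SVR 50% and 80%, a = 5% and b = 8%, (0.50 × 5 + 0.30 × 8) / 0.80 = 6.1%, ratio 1.2. A more extreme one (a = 2%, b = 15%) gives 3.4 to 5.9 over the same SVR pairs. The direction depends wholly on whether b is above or below a.

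In the non-null cells of the table, the approximate chance of a significant result at two-sided 5% is 7% to 14%. In the 3.0% against 7.0% example it is 13%.

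**Step 2: power.** For one SHIM arm against SOC, two-sided 5%, no clustering, everyone with SVR retested:

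power = Φ{(|p2 − p1| − 1.96 × se0) / se1}, with se0 from the pooled proportion and se1 from the separate proportions.

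With SVR 30% and 70%, n = 160 × 0.30 = 48 and 160 × 0.70 = 112. For 5% against 10%: pooled proportion 0.085, se0 = 0.0481, se1 = 0.0423, so power = Φ{(0.05 − 0.0943) / 0.0423} = 15%.

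| Patients with SVR, SOC / SHIM | 3% v 6% | 5% v 10% | 10% v 20% |
|---|---|---|---|
| 48 / 112 | 9% | 15% | 32% |
| 32 / 128 | 6% | 10% | 22% |
| 80 / 128 | 15% | 23% | 48% |
| 160 / 160 (ceiling: all cured and retested) | 25% | 40% | 71% |

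For 80% power, the three contrasts need 749, 435 and 199 patients with SVR per arm. A tripling from 5% to 15% would have 27% to 62% power in the first three rows. Clustering by clinic and missed tests lower every figure.

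**Step 3: event counts.** On a person-time scale, 40 weeks run from SVR12 to the 12-month test. With SVR 20–40% in SOC, person-years are 160 × 0.20 × 40/52 = 24.6 to 160 × 0.40 × 40/52 = 49.2. At 2 to 10 per 100 person-years that is 0.5 to 4.9 expected events. With SVR 60–80% in the two SHIM arms together (320 patients), person-years are 147.7 to 196.9, or 3 to 20 events. Counts this small make the normal approximation in Step 2 rough, but they lead to the same conclusion.

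**The case against.** The plan does not write an arm test for S3b. The mixed-model paragraph names its secondary outcomes ("The same approach will then be used for secondary individual outcomes (treatment motivation and adherence, treatment satisfaction, quality of life") and leaves re-infection out. The study hypotheses concern adoption, cascade outcomes and cure. Low power is openly disclosed, which is proper practice for a secondary endpoint. The Summary's list of secondary outcomes is not exhaustive (it also omits the interim cascade steps), so its silence on re-infection does not contradict 3.5.5. Restricting to SVR is inherent in the endpoint.

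All of this stands, and it limits the point. Several stronger readings are tempting but not supported:

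- **That S3b is tested with SOC as reference.** The referent clause is written for scale scores: "Mean scores will be normalized, with comparisons between the three groups, with the referent being SOC".
- **That S3b belongs to the Benjamini-Hochberg family.** Section 3.5.8 does not say which outcomes form that family.
- **That SHIM would look harmful.** This requires the additional patients cured by SHIM to be at higher risk of re-infection. The documents give no such evidence, and the reverse ordering makes SHIM look protective.
- **That a falsely significant finding is likely.** With so few events it is not. The more realistic risk is over-reading a point estimate or a non-significant result.

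The objection does not remove the two general testing sentences. S3b is a listed secondary endpoint and neither sentence excludes it. If no arm test is intended, the plan needs to say so.

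**Conclusion.** The point holds as a gap in the analysis plan. As written, 3.5.8 brings S3b under testing while the Summary treats it as something measured without adequate power. Any between-arm test would be made in a subset defined by P3 and would not be protected by randomisation, whichever way the bias runs.

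The size depends on the assumed risks: an apparent ratio of about 1.2 to 2.8, or 0.6 to 0.8 with the ordering reversed, and 1.00 only when the patients added by SHIM carry the same risk as the others. Power for a doubling stays below 50% in every scenario with SVR of 20–50% in SOC and 70–80% in SHIM. It reaches 71% only if every patient in both arms were cured and retested and the rates were as high as 10% and 20%. No primary endpoint, main hypothesis or sample size is affected. The change is worth making before analysis because it is cheap and prevents a contrast that cannot be interpreted.

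**What to change.** In section 3.5.8, state that S3b is exempt from both general testing sentences and is reported descriptively. For each arm give the number with SVR, the number retested, re-infection events, person-years from SVR12, and the rate with an exact 95% confidence interval, with no between-arm p-value. Add that the SVR groups are not randomised groups and that differences between them are not estimates of an intervention effect.

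If an arm comparison at 12 months is wanted, define a separate outcome: HCV RNA undetectable 12 months after treatment completion, with all enrolled patients as denominator, as for the cascade indicators. Patients not treated or without SVR count as not achieving it. Label it durable cure, because it answers a different question from re-infection and will be driven largely by P3. It also needs a stated rule for patients with SVR who have no 12-month result, since that test is only recommended and the schedule in 3.5.6 ends 12 weeks after treatment completion.

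The descriptive option costs a few sentences and the loss of a p-value with very little power. The durable-cure option also requires the missing-result rule and a 12-month entry in the schedule.

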## 1 Scientific Rationale

It is estimated that about 70 million people are infected with HCV globally [1], and the majority are not aware of their infection. HCV infection can persist undetected for many years before manifesting as chronic liver disease, cirrhosis, or liver cancer. HCV remains one of the leading infectious disease-related causes of death. Due to the recent advances in HCV treatment with direct acting antivirals (DAAs), more than 95% of treated patients can achieve sustained viral response (SVR). It can reverse the effects of early stage fibrosis and slow the progression of cirrhosis into decompensation or hepatocellular carcinoma [2, 3]. This reduces liver-related mortality by 20-fold and all-cause mortality by 4-fold [4].

Based on expert consensus in 2015, it was estimated that 3.7% (0.9-6.7%) of the population of Ukraine was infected with HCV and are viremic (RNA positive) viraemic [5]. By 2017, it is estimated that there were 1 368 300 individuals infected, majority with genotype 1 [6]. Of those infected, only 83,000 were registered in medical care, and about 35,000 are fully diagnosed and are on the waiting list at regional health authorities.

Availability of HCV treatment in Ukraine is growing. The Ministry of Health (MoH) procured ~40,000 DAA courses from 2019-2020 state budget. These medications were distributed to the facilities, and as of 12.2021 there were ~10,000 courses left. Additionally, ~7,500 courses will be procured from 2021 funds and delivered in 2022.

In addition, some regional governments and donor-funded projects are also procuring medications. These medications are distributed to specialized infectious disease hospitals, which diagnose and register patients and manage the waiting lists. Besides these programs (providing medications at no charge), some DAA medications recently became available for purchase through pharmacies. This indicates that in the next few years, the immediate treatment need (the waiting list) will be fully covered and **more intensive case detection and treatment enrollment efforts will be needed to continue the progress toward elimination.**

It is well known that people who inject drugs (PWID) have high burden of HCV [7] and due to multiple individual and structural barriers suffer from suboptimal access to accessing life-saving treatments. Enrollment into opioid agonist treatment (OAT), especially in integrated settings, is proven to improve health of opioid users through reducing drug use and increasing access to medical care [8-10]. Integration of OAT with HIV and TB care is well studied, including in Ukraine [10-12].

The scientific premise for integrating OAT and HCV services is strong. Recently injecting PWID and OAT patients have sufficient level of adherence and high rates of SVR [13-15]. Availability and effectiveness of new pangenotypic DAA formulations makes the notion of 'special populations' no longer pertinent. Several OAT-HCV care integration models have been evaluated in the DAA era with promising results [16-18], but no studies were conducted in low and middle-income countries.

There are around 17,000 patients currently receiving OAT in Ukraine, up to 83% of them are HCV-infected [19]. Due to stigmatization from medical providers and low awareness of recent guidelines, majority are not included in the DAA waiting lists, and due to low income cannot afford medications from pharmacies. The growing availability of DAA medications and ongoing healthcare reform context in Ukraine presents **a unique and time-sensitive opportunity to build and evaluate a simplified integrated HCV care model at OAT clinics, which can serve at least 9,000 patients in short-term.** Globally, the number of patients on OAT is increasing, and majority are treated at specialized addition treatment facilities [20]. A large number of these patients can benefit from integrated HCV services using a model we are proposing.

In our stage 1 project, we have developed and piloted a simplified HCV integrated management (SHIM) algorithm for OAT clinics. The uptake of HCV treatment and virologic outcomes using the SHIM algorithm in the pilot sample was high and consistent with reports of successful treatment outcomes among PWID

## 2 Goal and Aims

**The goal** of the proposed research is to evaluate feasibility and effectiveness of a simplified HCV care and treatment model integrated into OAT programs in Ukraine. **The simplified HCV integrated model (SHIM), if shown effective, would be relevant for other non-specialty healthcare facilities globally.** SHIM implementation will be strengthened by Project ECHO (Extension for Community Healthcare Outcomes), a collaborative telehealth learning process, supporting and empowering OAT clinicians to develop knowledge and self-efficacy about HCV care, which has not traditionally been considered integral to their scope of practice.

